12.5.7 CYP2A6

CYP2A6 activity at Day 1 (baseline) and Day 30 and change from baseline in CYP2A6 will be summarized by P3P variant and analyzed as a log-transformed variable, by sex and by product exposure category in the randomized population.

The data will be presented in the below outputs:

TFL number	Title
TABLES	
15.2.21.1	Descriptive Statistics of CYP2A6 activity – Randomized Population
15.2.21.2	Descriptive Statistics of CYP2A6 activity – By Sex - Randomized Population
15.2.21.3	Descriptive Statistics of CYP2A6 activity – By Product Exposure - Randomized Population
LISTINGS	
15.1.21.1	Listing of CYP2A6 Results

12.5.8 Weighing of P3P Products

For each timepoint (Day 1 and Day 30), the weight difference of P3P before and after use will be derived and presented by P3P variant, by sex and by product exposure category.

The data will be presented in the below outputs:

TFL number	Title
TABLES	
15.2.22.1	Descriptive Statistics of Weight of P3P before and after use – Day 1 and Day 30 - PK Population
15.2.22.2	Descriptive Statistics of Weight P3P of before and after use – Day 1 and Day 30 – By Sex - PK Population
15.2.22.3	Descriptive Statistics of Weight of P3P before and after use – Day 1 and Day 30 – By Product Exposure Category - PK Population
FIGURES	
15.3.4.1	Scatter Plot of PK AUC _(0-4h) versus P3P Weight difference By Puffing Behavior – Day 1 and Day 30 – PK Population
LISTINGS	
15.1.22.1	Listing Results of Weight of P3P before and after use – Day 1 and Day 30

12.5.9 Safety Evaluation

Safety variables monitored in this study include: AEs, vital signs (systolic and diastolic blood pressure, pulse rate, respiratory rate), spirometry, ECG data, concomitant medication, clinical chemistry, hematology, urine analysis safety panel, physical examination, respiratory symptoms (cough assessment VAS and Likert scales).

The primary analysis of Safety parameters will be conducted on the Safety population. All safety tables will be presented by variant and overall.

12.5.9.1 Safety Reporting

An exposure emergent AE is defined as an AE that occurs after first product use or that is present prior to first product use and becomes more severe after first product use. All other AEs will not be summarized but provided in listings only.

Any AEs which occur after ICF signature will be captured by the site collaborators and assessed by the Investigator or designee in order to establish relationship or relatedness in respect to study procedures. The AE listings will include all AEs captured in the database at any time during the study (including those from subjects who were not in the safety population). All AEs occurring after the product test use will be included in the summary tables. During the screening period prior to the first product use, only study procedure related AEs will be listed.

AEs reported from enrolled subjects, but who did not start use on day 1 or later will be summarized in a separate listing: “Enrolled but not started randomized product use AEs”. Furthermore AEs reported after discharge on Day 30 are summarized in a separate listing ‘Safety follow-up AEs’.

If there are more than 10 AEs, the tables will also be split by product exposure period. The product exposure periods will be defined as below

Partial dates will not be imputed, but assumptions will be made as follows to assign to exposure-emergent or not:

Date information	Assign as
Partial date, e.g., --May2012, or ----2011. If month/year is the same as, or later than the month and/or year of first product use	Exposure-emergent
Partial date, e.g., --May2012, or ----2011. If month and/or year is earlier than the month and/or year of first product use	Not exposure-emergent

If exposure emergent adverse events cannot be attributed to P3P due to e.g. missing start time, the worst case principle will be applied : i.e. the event will be allocated to P3P use.

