### 6.2.1 Admission (Day -1 – V2)

After enrollment, subjects will be required to perform product test by using up to 6 P3P products (alternating between P3P-1mg and P3P-2mg). In order to continue in the study, each subject will need to test at least one product of each P3P variant during the product test. Product test must be performed after the subjects have abstained from the use of any tobacco/nicotine containing products for at least 4 hours (4h wash-out period prior to product test). The product test period should be organized in a dedicated supervised area (i.e. not a dedicated cigarette smoking area). Subjects will be instructed on how to activate and use P3Pas specified in the P3P user guide. . They will be asked to puff with sufficient intensity to trigger the spinning of the capsule. The subject should hear the sound of the capsule spin and/or feel the vibration of the product induced by the spinning. Product test should end at least 10 hours prior to the start of product use for PK assessment on Day 1 (section [6.2.2](#))

After the product test, subjects not willing and/or unable to use P3P will be discontinued from the study and will enter a 14-day Safety Follow-Up Period.

At Day -1, after check-in on site, subjects will not be allowed to smoke cigarettes and/or use any other tobacco/nicotine containing products with the exception of P3P which can only be used during the product test period.

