### 12.3 Analysis Populations

Pharmacokinetic, pharmacodynamics, product acceptance, puffing/inhalation behavior endpoints will be analyzed using the PK population by actual product exposure and overall. Nicotine/tobacco containing product use, tobacco and nicotine containing product dependence, and CYP2A6 activity will be analyzed using the randomized population by actual product exposure and overall. Exposure to harmful and potentially harmful constituents will be analyzed using the randomized population. Safety will be analyzed using the safety population by actual product exposure and overall.

Actual product use exposure categories will be further defined in the SAP. Additional populations for sensitivity analysis could be defined in the SAP.

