4 ABBREVIATIONS AND DEFINITION OF TERMS

The following abbreviations are used within this SAP.

ABOUT	Assessment of behavioral outcomes related to tobacco and nicotine products
AE	Adverse event
ANOVA	Analysis of variance
ANCOVA	Analysis of covariance
ATC	Anatomical Therapeutic and Chemical
AUC	Area under the concentration-time curve
AUC _(0-4h)	Partial AUC, assessed between 0 and 4 hours post P3P use
BLOQ	Below the Lower limit of Quantification
BMI	Body mass index
BoExp	Biomarker of exposure
CEMA	2-cyanoethylmercapturic acid
CI	Confidence interval
C _{max}	Maximum concentration
COT	Cotinine
CRF	Case report form
CRO	Contract research organization
CTCAE	Common terminology criteria for adverse events and common toxicity criteria
CTMS	Clinical trial management system
CV	Coefficient of variation
CYP2A6	Cytochrome P450 2A6
DDE	Drug Dictionary Enhanced
ECG	Electrocardiogram
eCRF	Electronic Case Report Form
EOS	End of study
FEV ₁	Forced expiratory volume in 1 second
FVC	Forced vital capacity
HCOT	Trans-3'hydroxycotinine
HIV	Human immunodeficiency virus
HnB	Heat not Burn
HPHCs	Harmful and potentially harmful constituents
ICF	Informed consent form
ICH	International Conference on Harmonization
LLOQ	Lower limit of quantification
MedDRA	Medical dictionary for regulatory activities
PK	Pharmacokinetic(s)
PMPSA	Philip Morris Products S.A.
PT	Preferred Term
QTcB	QT Interval Corrected using Bazett's Formula

QTcF	QT Interval Corrected using Fridericia's Formula
RSR	Research Study Report
SAE	Serious adverse event
SAP	Statistical analysis plan
SD	Standard Deviation
SOC	System Organ Class
T	Time point
T ₀	Time point of start of product use
t _{max}	Time to maximum concentration
TFL	Tables, Figures, and Listings
Total NNAL	Total 4-(Methylnitrosamino)-1-(3-pyridyl)-1-butanol
ULOQ	Upper limit of quantification
VAS	Visual analogue scale
WBC	White blood cell (count)
WHO	World Health Organization
λ _z	Terminal elimination rate constant

The following special terms are used in this SAP:

Screen failure	Subject who signs the ICF but is not enrolled at Admission.
Enrollment	On Admission Visit (Day -1) for eligible subjects after all applicable inclusion and exclusion criteria have been satisfactorily assessed and met.
First product use time point	Start of the product test use.
Randomization	Allocation of the respective product, P3P-1mg or P3P-2mg, after product test on Day -1.

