11.1 Major Protocol Deviations

Subjects with major protocol deviations will be identified (at a population level) to determine whether they will be excluded from any of the analysis populations. The following have been identified as the major protocol deviations.

The categories for the major deviations will include, but are not limited to the deviations presented in Table 9.

Table 9: Definition of Major Protocol Deviations

Category	Description
Violation	Violation of inclusion/exclusion criteria (see below table)
Mis-randomization	Being administered the wrong product according to the randomization schedule during the entire exposure period
Mis-use of product (PK)	
Use of any nicotine or tobacco-containing product during the wash-out periods.Inadequate use of P3P product for PK assessment on D1 or D30 (eg. Product not used at all, product not pierced,...)
Concomitant medication	Medications within 5 half-lives of the drug prior to D1 or D30 with an impact on CYP2A6 activity
Visit missing	Subject did not attend a scheduled visit
GCP Deviation	Samples being analyzed in spite of written withdrawal of consent for analysis
Reporting of product use	Less than 75% of the daily product use reported in the e-diary over a period is available, or daily product use not reported over a period of more than 7 consecutive days

Violation of exclusion criteria 11 (Subject has received medication within 14 days or within 5 half-lives of the drug prior to Admission (whichever is longer) which has an impact on CYP2A6 activity) will be considered as preventing the evaluation of the primary objective. Such deviations will be considered as major and rendering the subject data non-evaluable for the primary objective.

Among the eligibility criteria, violations of inclusion criteria 2, 3 and 4, or of the exclusion criteria 10 will be assessed for their impact on the evaluability of the primary objectives during the pre-analysis data review meeting.

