12.1.3 Descriptive Statistics

All data will be presented in listings.

All endpoints will be summarized with descriptive statistics including number of subjects (n), number and percent of subjects with missing data, arithmetic means, 95% confidence intervals of the mean, and standard deviations (SD), median, first and third quartiles, minimum and maximum. Change from baseline will be added to the summary statistics when applicable.

For log normally distributed endpoints geometric mean, 95% confidence intervals of the geometric mean, geometric CV will be presented instead of arithmetic mean, 95% confidence intervals of the mean, and SD and percent change from baseline will be presented instead of change from baseline.

Categorical variables will be summarized by frequency statistics (number and percentage). For endpoints relating to sampling times (e.g., tmax) only median, first and third quartiles, and minimum and maximum will be presented.

Summary statistics and statistical analyses will be performed for subjects included in the relevant analysis population. For the calculation of summary statistics and statistical analysis, unrounded data will be used.

Summaries on Safety population will be produced by randomization group and overall, including the available data from subjects who tested the product but were not randomized.

The following product labels and descriptions will be used for the TFLs (Table 12):

Table 12: Product Labels

Randomization Group/P3P Variant	Format used in TFLs	Order in TFLs
P3P-1mg	P3P-1mg	1

P3P-2mgP3P-2mg

2

The following stratification labels (Table 13) for the TFLs will be used:

Table 13: Stratification Labels

Stratification Factor	
Sex	Male
	Female
Product Exposure Category	≤ 5 P3P/Day
	>5-10 P3P/Day
	>10 P3P/Day

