12.5.9.2 Adverse Events

A general summary table of AEs will be presented by P3P variant and overall, including:

- The number of events and the number and percentage of subjects reporting at least one AE.
- The number of events and the number and percentage of subjects reporting at least one SAE
- The number of events and the number and percentage of subjects reporting at least one investigational product –related AE, broken down by product relatedness (related to P3P) and expectedness (expected, not expected).
- The number of events and the number and percentage of subjects reporting at least one AE related to study procedure.
- The number of events and the number and percentage of subjects reporting at least one AE broken down by severity, including a subject once with worst severity.
- The number of events and the number and percentage of subjects reporting at least one AE leading to any action taken, broken down by action taken related to the product (combining the following items: product use interrupted, product use reduced, product use stopped), treatment given and any other action taken
- The number of events and the number and percentage of subjects reporting at least one AE leading to study discontinuation.

Additional summary tables of AEs will be presented by P3P variant (and period if more than 10 AEs) and overall, with a breakdown of the number of events, as well as the number and percentage of subjects reporting each AE, categorized by SOC and PT coded according to the MedDRA dictionary (version 22.0):

- The number of events and the number and percentage of subjects reporting at least one AE.
- The number of events and the number and percentage of subjects with at least one AE related to investigational product.
- The number of events and the number and percentage of subjects with at least one expected AE.

- The number of events and the number and percentage of subjects with at least one AE leading to product discontinuation.
- The number of events and the number and percentage of subjects with at least one AE related to study procedure.
- The number of events and the number and percentage of subjects with at least one AE by severity (mild, moderate, severe)

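### Adverse events from the pre-randomization product test, when subjects used both variants, are tabulated under the variant assigned afterwards, which narrows the descriptive between-variant difference

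*SAP*

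**What the plan says.** Protocol 6.2.1 has enrolled subjects perform a product test on Day -1, "using up to 6 P3P products (alternating between P3P-1mg and P3P-2mg"). A subject must try at least one product of each variant to continue. Randomization follows the test on the same day (SAP 4; Protocol 6.3), and the first randomized product is used on Day 1.

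SAP 12.5.9.1 sets the counting window: "An exposure emergent AE is defined as an AE that occurs after first product use", or one already present that then becomes more severe. SAP 4 defines the first product use time point as "Start of the product test use". SAP 12.5.9.1 adds: "All AEs occurring after the product test use will be included in the summary tables".

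For the columns, SAP 12.1.3 says: "Summaries on Safety population will be produced by randomization group and overall". Table 12 there provides only two product labels, one per variant. SAP 12.5.9.2 says: "A general summary table of AEs will be presented by P3P variant and overall".

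One provision works the other way. SAP 12.5.9.1 also splits the tables by product exposure period when there are more than 10 AEs, and Table 7 (SAP 7.9) lists the product test as a period of its own.

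**The concern.** The window opens before randomization, but the columns are defined by randomization. A cough or nausea that begins on Day -1, after products of both strengths, is reported under whichever variant the subject is later given. Such an event carries no information about that variant against the other.

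AEs are the main safety assessment (Protocol 12.6.3), and a reader will compare the two variant columns. Events unrelated to the allocation pull those columns together, so a real difference in tolerability looks smaller than it was. The counting rule in SAP 12.5.9.2 adds to this: a subject counts once per preferred term at the worst occurrence. A severe event from the test can therefore set that subject's severity under the assigned variant.

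**Working it through.** **Inputs from the documents.** 60 randomized subjects, 1:1, so 60/2 = 30 per variant (SAP 8). The sample size is empirical. No AE rate, effect size or power is given, so there is no planned figure to reproduce, and every rate below is an assumption.

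**Is the attribution real?**

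1. First product use is the start of the product test (SAP 4).
2. AEs after first product use are exposure-emergent and are summarized (SAP 12.5.9.1).
3. Allocation happens after the test (SAP 4).
4. Columns are by randomization group and overall (SAP 12.1.3, 12.5.9.2).

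Together these place a randomized subject's product-test AE in the column of the later allocation. The summary-table sentence could be read as covering only events after the test has ended. Even then, events arising between the end of the test and the first randomized use would be counted after exposure to both variants.

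**Size of the dilution.** Let q be the share of subjects with at least one product-test AE, with the same expectation in both arms because randomization comes later. Let p be the share with at least one AE from the first randomized use onward. Assuming independence:

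- tabulated incidence = 1 - (1-q)(1-p)
- tabulated difference = (1-q)(p2 - p1)

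With assumed p1 = 20% and p2 = 40%:

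| q | First column | Second column | Difference | Ratio |
|---|---|---|---|---|
| 0% | 20% | 40% | 20 points | 2.00 |
| 5% | 1 - 0.95×0.80 = 24% | 1 - 0.95×0.60 = 43% | 19 points | 1.79 |
| 10% | 1 - 0.90×0.80 = 28% | 1 - 0.90×0.60 = 46% | 18 points | 1.64 |
| 20% | 1 - 0.80×0.80 = 36% | 1 - 0.80×0.60 = 52% | 16 points | 1.44 |
| 30% | 1 - 0.70×0.80 = 44% | 1 - 0.70×0.60 = 58% | 14 points | 1.32 |

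**How often would the period split apply?** Treat the total AE count in 60 subjects as Poisson. The chance of more than 10 AEs is about 0.04, 0.65, 0.97 and above 0.999 at assumed means of 0.1, 0.2, 0.3 and 0.5 AEs per subject. In the table's own scenario, 30×0.20 + 30×0.40 = 18 subjects are expected to have an AE after randomization. The split would therefore probably be triggered if the threshold counts all AEs.

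**What the split leaves open.**

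- SAP 12.5.9.2 states it for the tables by system organ class and preferred term but not for the general table 15.2.23.1, which is also a topline output (SAP 13.2).
- SAP 12.5.9.1 does not say whether the threshold counts all AEs or the AEs in each table. It announces period definitions that do not follow there, so Table 7 has to be assumed.
- The split is additional, so the unsplit variant columns remain.
- Subject counts per period cannot be summed, because one subject may appear in several periods. The number of subjects per variant with any AE from Day 1 onward cannot be recovered from them.

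**The case against.** The strongest reply is that the SAP already deals with this. SAP 12.5.9.1 refers to the tables without limitation, the product test is a named period, and unless AEs are rare the threshold will be passed. That much stands: in most plausible scenarios a reader of the system organ class and preferred term tables will see the product-test events separately. It does not cover the general table with certainty, it lapses when AEs are few, and it does not correct the unsplit columns.

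It is also fair that the study is descriptive (SAP 5.3.1), that no claim rests on individual intervals (SAP 12.1.6), that no AE test is planned, and that table layout is left to a separate shell document (SAP 3). These limit the consequence. They do not change which events the variant columns contain.

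A reader might infer that a between-variant safety comparison is itself a secondary objective. Objective 4 is to assess safety and tolerability during the study and names no such comparison. A reader might also infer bias toward one variant. The test precedes randomization, so the added events have the same expectation in both arms: there is dilution and chance imbalance, not systematic bias.

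**Conclusion.** The point holds as a matter of tabulation. Followed as written, the SAP credits Day -1 events to a variant assigned afterwards, and the period split cures this only in part. The expected difference shrinks by (1-q). That is 1 to 6 points out of 20 for assumed q of 5% to 30% and assumed incidences of 20% against 40%, with independence of product-test and later AEs. The true size cannot be obtained from the documents. The overall column is unaffected.

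A wider reading is tempting because Protocol 12.3 says: "Safety will be analyzed using the safety population by actual product exposure and overall". A reader might take this as a promise to analyse by the variant actually used, which the SAP then breaks. The same protocol section leaves the exposure categories to the SAP, and SAP 12.1.7 defines them by average daily consumption (up to 5, above 5 to 10, above 10). The sentence therefore does not support that reading.

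**What to change.** In all AE tables, including 15.2.23.1 and whatever the number of AEs:

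- Add one pooled column, 'Product test (both variants)', for AEs with onset from the start of the product test until the first randomized use on Day 1.
- Base each variant column on AEs with onset, or worsening of an earlier AE, from that first randomized use. An event that began in the test and worsened later then appears in the pooled column by onset and in the variant column by worsening.
- Keep the overall column as planned.
- State that an AE whose onset cannot be placed before or after the first randomized use is counted in the variant column. The existing worst-case rule in SAP 12.5.9.1 only allocates such events to P3P use, which cannot choose between two columns that are both P3P.

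The cost is a few sentences in SAP 12.1.3, 12.5.9.1 and 12.5.9.2, one more column in the shells, and no new data collection. The drawback is a small number of events with uncertain timing, because Protocol 8.2.1 asks for onset times only where they can be obtained.

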12.5.9.2 Adverse Events

A general summary table of AEs will be presented by P3P variant and overall, including:

- The number of events and the number and percentage of subjects reporting at least one AE.
- The number of events and the number and percentage of subjects reporting at least one SAE
- The number of events and the number and percentage of subjects reporting at least one investigational product –related AE, broken down by product relatedness (related to P3P) and expectedness (expected, not expected).
- The number of events and the number and percentage of subjects reporting at least one AE related to study procedure.
- The number of events and the number and percentage of subjects reporting at least one AE broken down by severity, including a subject once with worst severity.
- The number of events and the number and percentage of subjects reporting at least one AE leading to any action taken, broken down by action taken related to the product (combining the following items: product use interrupted, product use reduced, product use stopped), treatment given and any other action taken
- The number of events and the number and percentage of subjects reporting at least one AE leading to study discontinuation.

Additional summary tables of AEs will be presented by P3P variant (and period if more than 10 AEs) and overall, with a breakdown of the number of events, as well as the number and percentage of subjects reporting each AE, categorized by SOC and PT coded according to the MedDRA dictionary (version 22.0):

- The number of events and the number and percentage of subjects reporting at least one AE.
- The number of events and the number and percentage of subjects with at least one AE related to investigational product.
- The number of events and the number and percentage of subjects with at least one expected AE.

- The number of events and the number and percentage of subjects with at least one AE leading to product discontinuation.
- The number of events and the number and percentage of subjects with at least one AE related to study procedure.
- The number of events and the number and percentage of subjects with at least one AE by severity (mild, moderate, severe)

If a subject has more than one occurrence of the same AE, the subject will be counted only once within a PT for each P3P variant, with the worst occurrence based on the presentation (e.g., for presentation by severity = most severe, for presentation by relationship = most related). Missing information on the intensity of AE will be counted as severe.

The data will be presented in the below outputs:

TFL number	Title
TABLES	
15.2.23.1	Summary of Adverse Events – Safety Population
15.2.23.2	Summary of Adverse Events by System Organ Class and Preferred Term – Safety Population
15.2.23.3	Summary of Adverse Events Related to Investigational Product by System Organ Class and Preferred Term - Safety Population
15.2.23.4	Summary of Adverse Events Related to Study Procedures by System Organ Class and Preferred Term - Safety Population
15.2.23.5	Summary of Expected Adverse Events by System Organ Class and Preferred Term
15.2.23.6	Summary of Adverse Events by System Organ Class, Preferred Term and Severity – Safety Population
15.2.23.7	Summary of Adverse Events Leading to Investigational Product Discontinuation by System Organ Class and Preferred Term – Safety Population
15.2.23.8	Summary of Adverse Events Leading to Study Discontinuation by System Organ Class and Preferred Term – Safety Population
LISTINGS	
15.1.23.1	Listing of Exposure Emergent Adverse Events
15.1.23.2	Enrolled but not started randomized product use AEs
15.1.23.3	Safety follow-up AEs
15.1.23.4	Listing of AEs leading to study discontinuation

